4.4 Subject withdrawal

Participants can withdraw from the study at any time and without consequences for participating in the rehabilitation program or other clinical care. In case of withdrawal, the study subject may be replaced.

5 CONTENT OF THE REHABILITATION PROGRAM

Development of the application

The application is not a clinical device but a communication tool between healthcare providers and patients. The rehabilitation program is developed by a team of TYKS healthcare workers of multiple disciplines in tight collaboration with HealthFOX. The multidisciplinary team included three pulmonologists (MK, MF, HS), one physiotherapist, two nutritional therapists, and one nurse specialized in smoking cessation.

Content of the rehabilitation program

Patients receive patient education materials throughout the program in text and video formats. These materials provide information on COPD management, lifestyle modifications, and strategies to enhance their well-being. Furthermore, the program contains an individually tailored exercise program., consisting of the following phases:

i. **Phase 1: Patient Assessment and Questionnaires**

- a. Patients are enrolled in the digital COPD therapeutics program through a referral from their healthcare provider or self-enrolment.
- b. Patients are prompted to complete a series of validated questionnaires and assessments, including:
 - i. CAT (COPD Assessment Test) questionnaire to assess their symptom severity.
 - ii. St George respiratory questionnaire, Finnish version
 - iii. Nutrition risk screening questionnaire (NRS2002) to evaluate their dietary habits and nutritional status.
 - iv. Physical activity participation questionnaire (unvalidated questionnaire that is currently used in TYKS clinical setting to score their current level of physical activity).
 - v. Smoking (Standardised nicotine dependence questionnaire, and stop smoking questionnaire) and alcohol question to assess their tobacco and alcohol consumption.
 - vi. Depression scale (DEPS) to screen for depression

ii. **Phase 2: Clinical Input and Evaluation**

- a. Review of clinical parameters by a medical doctor, including:
 - i. Pulmonary function test results (including spirometry)
 - ii. 6-minutes walking test

- iii. Blood test results, including hemoglobin, albumin, C-reactive protein, partial pressure of CO₂ (PCO₂).
- iv. Electrocardiogram
- v. Medication history
- vi. Current medications
- vii. And other relevant medical data.

- b. The combination of patient input and clinical parameters is used to individualize the COPD therapeutics program for each patient. This will be done by the study investigators and healthcare professionals, and parts will be automatized. The automatically generated aspects will be evaluated and, if needed, adjusted by the study investigators and/or healthcare professionals.

- iii. **Phase 3: Individualized Program Development**
 - a. Patients who are identified as smokers are provided with a Cognitive Behavioural Therapy (CBT)-based program to support smoking cessation.
 - b. Based on the risk profile, participants are assigned to different types of breathing exercises, which are timed and progressively increased in intensity over time to improve lung function.
- iv. **Phase 4: Nutritional Advice**
 - a. Patients receive personalized nutritional advice based on **their input and nutritional status assessment**. The program aims to improve their dietary habits and overall nutritional status.
- v. **Phase 5: Physical Activity Program Initiation**
 - a. a physical activity program will start in the fifth week of the program. The intensity and duration of the program are determined based on their 6-minute walk test results according to the guidelines of the American College of Sports Medicine (ACSM) as applied in routine medical practice. Each patient receives an individually tailored program, which is approved by the TYKS physiotherapist. (11)
 - b. Over time, the program gradually increases the intensity and duration of the walking program to help patients build endurance.
- vi. **Phase 6: Strength Training**
 - a. After approximately eight weeks in the program, **depending on patients' clinical parameters** patients are introduced to strength training exercises to improve their overall physical strength and quality of life. Progression is slow and builds over time based on their risk profile.
- vii. **Phase 7: completing the program and follow-up**

- a. The training program finishes after 14 weeks. In this phase, the patient is interviewed about their experience
- b. In weeks 16 (+/- 2 weeks) and 26 (+/- 2 weeks), the symptoms will be scored with mMRC and St George respiratory questionnaire. In addition, a 6-minute walking test will be repeated in week 26 (+/- 2 weeks).

Tailoring of the program at the individual level

Regular monitoring by the digital care-master (COPD expert nurse/physiotherapist) will ensure patient adherence to care, follow-up on progress and adjust the program if needed based on their evolving needs and goals or make referral back to the clinical team (TF, MK, HS, RL)

Gradual Program Advancement

As the program is rolled out, its content may be adjusted based on clinical experience and patient feedback from and beyond this pilot study.

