2 STUDY OBJECTIVES AND PURPOSE

The general objectives of this pilot study are:

- To facilitate a safe rollout of the remote rehabilitation program for COPD patients in Southwest Finland.
- To identify and subsequently improve limitations of the rehabilitation program.
- To evaluate the levels of participant engagement and adherence to the digital COPD rehabilitation program over an extended period to understand its sustainability and long-term impact.
- To determine the effectiveness of the digital COPD rehabilitation program in improving lung function, exercise capacity, and quality of life among participants
- To assess the impact of the digital program on healthcare resource utilization, including hospital readmissions, emergency room visits, and outpatient visits related to COPD management.
- To measure participant satisfaction, usability, and overall experience with the digital platform to identify areas for improvement and enhance user engagement.
- To evaluate the cost-effectiveness of implementing the digital program compared to conventional rehabilitation methods, considering direct healthcare costs.

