3.2 General study outline and study schedule

Study subjects will be recruited from the 15th of April 2024 to the 30th of June 2026.

The rehabilitation program will be initiated preferably within one week but, at the latest within, 4 weeks from signing an informed consent, and the program will last up to 12 weeks. Follow-up will include 1 distant evaluation (questionnaires) at week 16 and a final visit at 26 weeks (+/- 2 weeks), including a 6-minute walking test. Follow-up may last up to 28 weeks from recruitment.

The final study report will be written in the years 2026-2027.

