8.4 Qualitative analyses

The study will also gather qualitative data through focus group discussions with patients of 8-10 participants per group will be included and will continue until data saturation is reached. Discussions with healthcare professionals will be based on availability and might be one-on-one depending on doctor's schedules. These discussions delve into subjective experiences, perceptions, and perspectives regarding the digital COPD rehabilitation program. Patient discussions will explore their engagement, challenges faced, and perceived benefits, shedding light on the program's usability and impact on daily life. Simultaneously, interviews with healthcare providers will capture insights into the program's integration into clinical practice, perceived patient response, and potential areas for program enhancement. These qualitative interviews will provide a nuanced understanding of participant experiences and healthcare provider perspectives, enriching the study's findings beyond quantitative measures.

The qualitative data will be analyzed using ATLAS.ti, a robust qualitative data analysis software. The software enables systematic coding and organization of textual and multimedia data, allowing for in-depth exploration and interpretation. Initially, the interview transcripts will be imported into ATLAS.ti and a systematic coding process will be employed to identify themes, patterns, and key concepts within the data. Through iterative coding and categorization, codes will be grouped to form themes and sub-themes, fostering a comprehensive understanding of participant perspectives and

experiences. The software's tools for qualitative analysis, such as network views and query functions, will be utilized to uncover relationships between codes and themes, facilitating the synthesis of rich, contextual insights from the qualitative data collected during the interviews.

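### The only individual patient experience interview is tied to programme completion, and neither it nor the focus groups provides for patients who stop early, so the experience findings risk completer bias

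*Protocol*

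**What the plan says.** Section 2 of the protocol lists among its objectives "To identify and subsequently improve limitations of the rehabilitation program" and "To measure participant satisfaction, usability, and overall experience with the digital platform". Neither is restricted to patients who finish.

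Section 5 describes the programme in seven phases. The individual interview appears only in Phase 7, the phase for finishing the programme and follow-up. Its first sentence is "The training program finishes after 14 weeks" and its second is "In this phase, the patient is interviewed about their experience". Section 3.2 gives a different length: "the program will last up to 12 weeks".

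Section 8.4 plans "focus group discussions with patients of 8-10 participants per group will be included and will continue until data saturation is reached". On content it says "Patient discussions will explore their engagement, challenges faced, and perceived benefits", and the same sentence goes on to usability. It adds that "interviews with healthcare providers will capture insights into the program's integration into clinical practice, perceived patient response, and potential areas for program enhancement".

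Section 4.4 covers withdrawal from the study and allows replacement. Section 6.1 lists participant satisfaction among the other outcomes, with no instrument or time point.

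**The concern.** The interview comes at the end of a programme that asks more of patients as it goes on: physical activity starts in week five and strength training after about eight weeks. A patient who gives up the application in the first weeks, or when walking begins, may have the clearest account of what did not work. The plan does not arrange to ask that patient at the time.

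At stake are the objectives on limitations, satisfaction and usability. If those who answer are mainly those who finished, the programme may look more usable and better liked than it was for everyone who started, and its reasons for failure may go unrecorded. Focus groups can reach saturation within the set of people sampled without anyone having explained why they stopped. The gap cannot be closed at analysis, because an account that was never collected cannot be reconstructed.

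**Working it through.** The protocol states no stopping rate, satisfaction target or expected interview count, so there is no figure to reproduce. The check is to go through each possible source of patient experience and ask whether it provides for a patient who stops early.

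1. **Individual interview (Section 5, Phase 7).** It is set after training ends. No other time point is given and no interview is triggered by stopping.
2. **Patient focus groups (Section 8.4).** Groups of 8-10 continue until saturation. They are not limited to completers, but nothing requires or invites people who stopped.
3. **Interviews with professionals (Section 8.4).** They cover patient response as the professional perceives it, which is a proxy for the patient's own account.
4. **Care-master monitoring (Section 5, tailoring).** It serves adherence, adjustment and referral back. Recording experience or reasons for stopping as study data is not described.
5. **Patient feedback (Section 5, programme advancement).** It may lead to changes in content, but no collection procedure is given.
6. **Weeks 16 and 26 (Section 5, Phase 7).** Symptom scores are taken at both and a walking test at week 26. No experience measure is listed.
7. **Satisfaction outcome (Section 6.1).** No instrument or time is given.
8. **Withdrawal (Section 4.4).** It concerns leaving the study, not stopping the programme. No contact about reasons is stated. Replacement is allowed, which can shift a sample of at most 50 (Section 4.2) further towards those who stay.

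No source provides explicitly for early stoppers. Sources 2 to 5 leave room for them.

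**Delay.** Suppose a patient stops when physical activity begins in week five and is still interviewed in Phase 7. The wait is about 14 - 5 = 9 weeks on the Section 5 length, or up to 12 - 5 = 7 weeks on the Section 3.2 length. The two lengths must be reconciled in any case, because the interview time depends on them.

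**What can be said on size.** Let *d* be the share of patients who give no experience data and *p* the proportion satisfied among those heard. The proportion satisfied among all patients lies between *p*(1 - *d*) and *p*(1 - *d*) + *d*, a range of width *d*. Both inputs are assumptions. With *p* = 0.90 and 50 patients:

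| Assumed *d* | Patients heard | Lower bound | Upper bound |
|---|---|---|---|
| 0.10 | 45 | 0.90 × 0.90 = 0.81 | 0.81 + 0.10 = 0.91 |
| 0.20 | 40 | 0.90 × 0.80 = 0.72 | 0.72 + 0.20 = 0.92 |
| 0.30 | 35 | 0.90 × 0.70 = 0.63 | 0.63 + 0.30 = 0.93 |

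These ranges apply only if the study reports a proportion satisfied and early stoppers supply nothing from any source. The protocol states neither.

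**The case against.** The strongest reply is that this rests on silence. Phase 7 also holds the week 16 and week 26 assessments, and nothing makes these or the interview conditional on having finished training. Section 4.4 keeps study and programme participation apart, so a patient who leaves the application can remain in the study and be interviewed. The focus groups, the professional interviews and the feedback during the programme are not limited to completers. Focus-group sampling and interview timing are often left to an interview guide, and this is a descriptive pilot.

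Much of this stands, and it rules out three stronger readings.

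- A reader might infer that early stoppers are not interviewed and that the objectives are answered by completers alone. The protocol does not say so; it only fails to provide for early stoppers.
- A reader might put a figure on the overstatement. It would be the stopping share times the gap in satisfaction between completers and stoppers, and the protocol gives neither. A 10-point gap with 20% stopping gives 0.20 × 10 = 2 points; a 50-point gap with 40% stopping gives 0.40 × 50 = 20 points. The answer is set by the assumptions.
- A reader might infer that the roll-out depends on these data. Sections 1 and 11.2 have the programme entering routine care in 2024 in any case, and the continuation appraisals in Sections 7 and 8.5 concern safety.

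What does not stand is that this is mere missing detail. The protocol fixes when the interview is held, and that timing suits patients who finish. An analysis plan cannot supply data that were not collected.

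**Conclusion.** The concern holds as a risk of completer bias. The only individual experience interview is tied to the completion phase, and neither it nor the focus groups provides for patients who stop early, although the objectives on limitations, satisfaction and usability cover all participants. The likely direction is towards a favourable picture, on the assumption that those who stop are less satisfied than those who finish. The size cannot be derived from the protocol. The importance is moderate: the primary walking-test outcome is untouched, but the weakness bears directly on stated aims of the pilot and is inexpensive to remove.

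**What to change.** - **Section 5, Phase 7:** offer the same experience interview, with the reason for stopping, when a patient stops the programme or at completion, whichever comes first. Allow it by telephone or through the application.
- **Section 8.4:** invite early stoppers to the focus groups or to individual interviews before saturation is declared.
- **Reporting:** present experience and satisfaction by completion status, with the number in each group who were not interviewed.
- **Sections 3.2 and 5:** reconcile the two programme lengths so that the time of the completion interview is clear.

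The cost is a few interviews held at a different time. No new instrument or additional patients are needed, and the regular monitoring in Section 5 gives an occasion to notice that a patient has stopped. Some of those who stop will decline, so coverage will be incomplete; reporting their number shows how incomplete.

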6 OUTCOME VARIABLES

6.1 Assessment of efficacy

The single primary outcome measurement is distance in the 6 minutes walking test at 16 weeks in comparison to baseline to assess efficacy at the individual level. Secondary outcome includes 6 minutes walking test result at week 26 and St George Respiratory Questionnaire and 6 minutes walking test after 16 weeks and after 26 weeks in comparison to the result before initiation of the program. Other outcome measurements include the participant satisfaction, and other quantitative and qualitative measures of respiratory health and well-being.

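### The single primary outcome is a week-16 walk test, but the schedule has no walk test at week 16

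*Protocol*

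**What the plan says.** Section 6.1 names one primary outcome: "The single primary outcome measurement is distance in the 6 minutes walking test at 16 weeks in comparison to baseline". Its next sentence asks for the week-16 walk again among the secondary outcomes: "6 minutes walking test after 16 weeks and after 26 weeks in comparison to the result before initiation of the program".

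Section 3.2 describes the visits: "Follow-up will include 1 distant evaluation (questionnaires) at week 16 and a final visit at 26 weeks". It attaches a walk test to the final visit only.

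Section 5, Phase 7, gives the same schedule in more detail: "In weeks 16 (+/- 2 weeks) and 26 (+/- 2 weeks), the symptoms will be scored with mMRC and St George respiratory questionnaire". The walk test then appears separately: "In addition, a 6-minute walking test will be repeated in week 26 (+/- 2 weeks". The step at the end of training names only an interview. The baseline walk test is listed in section 5, Phase 2.

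Section 8.3 plans a significance test of the primary outcome at the 0.05 level.

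**The concern.** Section 6.1 needs a measurement at week 16 that sections 3.2 and 5 do not provide. The conflict is hard to put down to a slip of one word: section 6.1 asks for the week-16 walk twice, and the two schedule sections agree with each other in leaving it out.

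If staff follow the schedule, no patient has a planned value for the primary outcome, and a walk test missed at week 16 cannot be recovered later. The obvious substitute, the week-26 walk, answers a different question, because it is taken much longer after training ends. If the protocol is left as it is, the choice of which walk counts as primary falls to the analysis stage, possibly with results known.

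**Working it through.** No statistical figure is at issue, so the check compares the sections and then the windows.

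**1. Walk tests by time point**

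| Time point | Section 6.1 | Section 3.2 | Section 5 |
|---|---|---|---|
| Baseline | comparator | not listed | walk test (Phase 2) |
| End of training | none | none | interview only (Phase 7) |
| Week 16 | walk test, primary and again secondary | remote questionnaires | mMRC and St George questionnaire |
| Week 26 | walk test, secondary | walk test | walk test, mMRC and St George questionnaire |

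Scheduled follow-up walk tests: 1, at week 26. Scheduled walk tests at week 16: 0.

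**2. Could the week-26 test count as a late week-16 test?** Section 5 gives both time points a window of +/- 2 weeks.

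- Week 16: 16 - 2 = 14 to 16 + 2 = 18.
- Week 26: 26 - 2 = 24 to 26 + 2 = 28.
- Nominal gap: 26 - 16 = 10 weeks. Smallest gap on a common clock: 24 - 18 = 6 weeks.
- Least favourable mixed clock: week 16 counted from program start after the longest delay in section 3.2 (4 weeks), week 26 counted from consent. The week-16 window then ends at 18 + 4 = 22 weeks from consent, still 24 - 22 = 2 weeks before the week-26 window opens.

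The windows do not overlap on any of these readings.

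**3. How different are the two time points?** Weeks after program end = visit week - (program length + start delay). The protocol gives two program lengths: "the program will last up to 12 weeks" in section 3.2 and "The training program finishes after 14 weeks" in section 5. Both are carried through.

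| Weeks counted from | Visit | Nominal | With +/- 2 window |
|---|---|---|---|
| Program start (delay 0) | 16 | 16 - 14 = 2 to 16 - 12 = 4 | 14 - 14 = 0 to 18 - 12 = 6 |
| Program start (delay 0) | 26 | 26 - 14 = 12 to 26 - 12 = 14 | 24 - 14 = 10 to 28 - 12 = 16 |
| Recruitment (delay 0 to 4) | 16 | 16 - 18 = -2 to 16 - 12 = 4 | 14 - 18 = -4 to 18 - 12 = 6 |
| Recruitment (delay 0 to 4) | 26 | 26 - 18 = 8 to 26 - 12 = 14 | 24 - 18 = 6 to 28 - 12 = 16 |

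Section 3.2 treats 12 weeks as a maximum, so a shorter program would raise the upper limits. On nominal weeks, week 16 lies around or shortly after program end, and week 26 two to three months or more after it.

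**4. Dates for the first possible recruit** (recruitment opens 15 April 2024, section 3.2; weeks counted from recruitment)

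- Week-16 window closes: 15 April 2024 + 18 weeks = 19 August 2024.
- Week-26 window opens: 15 April 2024 + 24 weeks = 30 September 2024.
- Counting from program start moves each date up to 4 weeks later.

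**The case against.** Nothing in the text shown removes the conflict, but several points limit it.

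- **A week-16 walk may exist anyway.** Section 3.2 says what follow-up will include, which is not strictly an exhaustive list, and section 10.1 also draws data from patient records and a COPD registry. A routine walk test near week 16 is therefore possible. This stands as a limit on the harm. But such values would be unscheduled and possibly selective, and section 5 sets the repeat walk apart as belonging to week 26.
- **The patient information sheet is not shown.** It might reveal which time point was intended. It would not remove the conflict between the sections.
- **Sections 3.2 and 5 agree on the walk test, so only 6.1 is out of line.** That is correct, but agreement between two sections does not prove that 6.1 is the one in error.
- **The clock is not wholly open.** Section 3.2 limits follow-up to 28 weeks from recruitment, which equals 26 + 2 and favours counting from recruitment. This bears on the weeks after program end, not on the missing test.
- **It is a pilot.** The study has one arm and is mostly descriptive, which lowers the stakes. It still names one primary outcome and tests it.

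**Conclusion.** The contradiction is real and should be corrected. Followed as written, the schedule leaves the only primary outcome without a planned follow-up measurement in any of the up to 50 patients. The 6-week separation of the windows assumes one clock for both visits; the mixed clock narrows it to 2 weeks without closing it. The conclusion depends on sections 3.2 and 5 being followed as they stand. It does not depend on any effect size, variance or power figure.

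A lesser drafting fault lies in section 6.1: "Secondary outcome includes 6 minutes walking test result at week 26 and St George Respiratory Questionnaire and 6 minutes walking test after 16 weeks". The week-16 walk is thus both primary and secondary, and the week-26 walk appears to be listed twice, although that second point depends partly on how the sentence is read.

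**What to change.** Reconcile sections 3.2, 5 and 6.1 by a protocol amendment made before any follow-up walk results are examined. If results have already been examined, say so in the amendment and in the report. Section 9.3 requires submission to the Ethical Committee for either option.

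**Option A: move the primary outcome to week 26.** In section 6.1, define it as the change in 6-minute walk distance from baseline to week 26 (+/- 2 weeks). Remove the week-16 and week-26 walks from the secondary outcomes and keep the St George questionnaire at weeks 16 and 26 as secondary. This adds no procedure. The cost is a changed question: maintained effect some 12 to 14 weeks after the program ends (8 to 14 if weeks count from recruitment; nominal visit weeks), not effect shortly after it. Week-26 results may exist from about 30 September 2024, so its credibility rests on the timing condition above.

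**Option B: keep week 16.** Add a week-16 visit (+/- 2 weeks) with a walk test to section 3.2 and make section 5 consistent. List the week-26 walk once as secondary and delete the duplicate week-16 walk. The cost is one extra visit per patient. Patients already past week 18 when the amendment takes effect (from about 19 August 2024 for the first possible recruit) would have no primary value unless the test was done outside the schedule.

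Under either option, state whether weeks count from recruitment or from program start, and reconcile the two program lengths in sections 3.2 and 5, since together they fix what each time point means.
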